9. STUDY OUTCOMES

9a. Primary Outcome

Occurrence and severity of complications arising from cryoablation treatment

9b. Secondary Outcome(s)

1. Occurrence and causes of procedural/technical failure of the procedure

2. Where relevant, change in maximal diameter of lesion following treatment, as measured on ultrasound or MRI, comparing pre-treatment diameter to diameter at 2 years.
3. Where relevant, change in symptomatology post treatment, as assessed by quality of life questionnaires and visual analog scales.
4. Where relevant, change in function post treatment, as assessed by clinical review and physiotherapy assessment.

10. STUDY PROCEDURES

10a. Recruitment of participants

Data from all cryoablation procedures performed in our institution will be entered into the registry. Data from procedures at other UK institutions may also be submitted.

10b. Randomisation

This is a non-randomised study.

10c. Study procedure

Data will be entered into an online-based registry designed for this study. The registry is designed and managed by Obsidian Health Ltd and funded by Biocompatibles UK Ltd.

The following dataset is an indication of the data items that will be collected within the registry. The registry is not limited to these items and the items and data format can be changed before or during the registry.

Schema

- Patient
- Patient has Diagnosis
- Patient has one or more Treatments
- Patient has one or more Follow-ups
- Patient has one or more Complications
- Patient has one or more Post-ops

Data items

Data item	Data type
-----------	-----------

Patient

Patient identifier	Local pseudonym
Date of Birth (0 - 18)	Month and year only
Gender	List
Weight (Kg)	Float

ASA score (anaesthetic risk) 1 - 4	Integer
---------------------------------------	---------

Diagnosis

Diagnosis	List
Comorbidities	List
Biopsy proven?	Y/N
Snomed code	List
Lesion anatomical site: limb, thorax, head and neck, abdomen, pelvis (need more detail here)	List
Lesion tissue involvement: Fat/bone/muscle/other	List
Pre-operative information	
Length of symptoms already	Months
Imaging (MRI, US, other)	List
Symptoms	List
Other treatments tried	List
Treatment	
Treatment date	Date
Pre-op	List
Size of lesion	Float [possibly 3 floats]
Symptoms	List
No of probes	Integer
Freeze time*	Float
Thaw time*	Float
Cryoablation system probe type(s)	List [may need updating as new systems come onto market]
No. of freeze/thaw cycles	Radio
Thaw type [active or passive]	Radio
% power during freeze cycle	
*freeze and thaw time for each cycle	

Technical success	Binary
If technical success no - reason	List +/- text
Length of inpatient stay	
Any medical support required (list, such as iv analgesia)	
Immediate complications	Multi-list
Follow-up at 3 mths, 6 mths, 1 year, 2 years	
Follow-up date	Date
Imaging	List
Size of lesion	Float
Symptoms	List
Complications at follow up	
Complication	Multi-list
Onset	
Duration of problem	
Any treatment given	
Resolved?	

10e. Patient safety

Any adverse events related to a cryoablation procedure will be medically managed as per clinical need. All such events will be recorded, reported and managed according to the institution's risk management system, alongside any data collection pertaining to this study.

10f. Adverse events, Serious Adverse Events and Product Malfunctions

An adverse event (AE) is defined as any untoward or unfavourable medical occurrence in a human patient or clinical trial subject administered a medicinal product, including any abnormal sign (for example, abnormal physical exam or laboratory finding), symptom, or disease, temporally associated with the patient's participation in the research, and which does not necessarily have a causal relationship with this treatment (study medication, application of the study device, etc.) or study participation. It includes all adverse events regardless of seriousness or relatedness.

A serious adverse event (SAE) is defined as an adverse event that

- a) Results in death

- b) Led to a serious deterioration in health that either:
 - I. Results in a life-threatening illness or injury, or
 - II. Results in a permanent impairment of a body structure or a body function, or
 - III. Requires in-patient hospitalization or prolongation of existing hospitalization, or
 - IV. Results in medical or surgical intervention to prevent life threatening illness or injury or permanent impairment to a body structure or a body function.
 - V. Results in a persistent or significant disability/incapacity or substantial disruption of the ability to conduct normal life functions.
- c) Led to fetal distress, foetal death or a congenital abnormality or birth defect

A product malfunction is defined as a failure of the device to meet its performance specifications, essential function or otherwise perform as intended. Performance specifications include all claims made in the labelling for the device. The essential function of a device refers not only to the device's labelled use, but for any use widely prescribed within the practice of medicine.

Reporting of Adverse Events, Serious Adverse Events and Device Malfunctions

The Institution and/or the Sponsor-Investigator shall report all and any serious adverse events, product malfunctions or quality complaints (regardless of causality) that they become aware of in relation to the Product and/or the investigation to BTG.

All reports will be exchanged in English and Sponsor-Investigator will also provide BTG with such information and reasonable assistance as may be requested by BTG to allow BTG to comply with their obligations.

The Institution and/or the Sponsor-Investigator shall report all SAEs and incidents impacting patient safety to [contact].

SAEs

The Sponsor-Investigator will report SAEs within **one business day** to enable BTG to comply with their obligations as the device manufacturer, under applicable laws and regulations.

All reports will contain the following, if available:

- Study title and name of the Sponsor-Investigator.
- Patient number
- Adverse event number
- Date of event occurrence/date notified
- Product details
 - Product name/ part number
 - Size / dose
 - Batch / lot number
- Adverse event details along with comprehensive event description
- Action(s) taken to treat or resolve the event

- Outcome
- Investigators opinion of causality of event i.e. related to
 - Drug
 - Device
 - Procedure
- Product returned to **Galil** if applicable

Device Malfunctions

The Institution and/or the Sponsor-Investigator shall report all device malfunctions and/or quality complaints to [contact] within one business day of becoming aware of the issue.

10g. Data monitoring

Data will be reviewed by the co-investigators at a minimum of 6 month intervals. Procedural data will be collected for 3 years and follow up data will continue to be collected for a further 2 years. The registry plans to close after 5 years but this could be extended. Data analysis will be completed by 6 months post closure of the registry.

See Appendix 1 [Obsidian Data Security Protocol] for details of data storage and management by Obsidian Health Ltd.

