4. OBJECTIVES

1. To identify all cryoablation procedures in children in our institution.
2. Invite other centres offering cryoablation in children to participate by submitting data via the online registry
3. To collect data via an online registry
4. To analyse the data to establish the safety and efficacy of this procedure in children and to identify trends in outcomes for different conditions treated
5. To establish guidelines for best practice regarding cryoablation treatment in children

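### The stated registry schema ties no treatment, follow-up or complication to a lesion, so outcomes of children treated for several lesions cannot be reliably assigned to site or condition

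*Protocol*

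**What the plan says.** Protocol section 10c gives a schema and a list of data items. The schema has a line for diagnosis, "Patient has Diagnosis", and separate lines for the repeating records, among them "Patient has one or more Treatments", "Patient has one or more Follow-ups" and "Patient has one or more Complications".

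The items that describe the lesion sit under Diagnosis: the diagnosis itself, SNOMED code, biopsy status, "Lesion anatomical site: limb, thorax, head and neck, abdomen, pelvis (need more detail here" (the authors' own open note) and "Lesion tissue involvement: Fat/bone/muscle/other". The only lesion descriptors in the treatment and follow-up items are "Size of lesion" and symptoms.

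The same section says the list is indicative and may be altered before or while the registry runs. Section 5 describes a registry in which treatment may be repeated. Objective 4 in section 4 includes a wish to "identify trends in outcomes for different conditions treated". Secondary outcome 2 in section 9b compares maximal lesion diameter before treatment with that at 2 years. Section 11 promises univariate and multivariate analysis and gives no rule for linking records.

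**The concern.** Trends by condition need the condition treated at each procedure. Change in diameter needs the same lesion measured twice. Both are properties of a lesion, but the stated structure hangs everything on the child. When a child has one lesion, child and lesion coincide and nothing is lost. When a child has two, the treatment record does not say which was treated, the follow-up record does not say which was measured, and the complication record does not say which procedure it followed.

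A later analysis plan can choose the unit of analysis, but it cannot supply a field that the database does not hold. That is why the point belongs to the design of the registry.

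**Working it through.** The protocol gives no figure to reproduce, so the check sets the records in section 10c side by side.

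| Record | Number per child as written | Main items | Names a lesion, site or diagnosis? |
|---|---|---|---|
| Diagnosis | singular, no limit stated | diagnosis, comorbidities, biopsy status, SNOMED code, site, tissue | yes, but not tied to any treatment |
| Treatment | one or more | date, lesion size, symptoms, probes, freeze and thaw settings | no |
| Follow-up | one or more | date, imaging, lesion size, symptoms | no |
| Complication at follow-up | one or more | complication, onset, duration, treatment given, whether resolved | no, and no procedure named |

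Technical success and immediate complications are printed after the treatment items. Even if they belong to the treatment record, that record does not name its lesion.

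Taking the possible cases in turn:

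1. **One lesion, treated once.** Site and condition are known. No loss.
2. **One lesion, treated again.** One diagnosis entry serves every treatment. Site and condition are still known.
3. **Two lesions, same diagnosis, different sites.** Condition is known. Site and tissue cannot be assigned to a procedure, and sizes cannot be matched to a lesion. If both lesions fall in the same broad site category, such as limb, the site grouping also survives.
4. **Two lesions, different diagnoses.** Neither condition nor site can be assigned to a procedure, a size or a complication.

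For the diameter outcome in cases 3 and 4, let the pre-treatment sizes be a1 and a2 and the 2-year sizes b1 and b2, with no lesion label. The data allow two pairings:

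- changes of b1 − a1 and b2 − a2;
- changes of b2 − a1 and b1 − a2.

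The child's mean change is (b1 + b2 − a1 − a2)/2 under both. The change for each lesion differs between them, and so does any summary by condition or site.

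The proportion of children in cases 3 and 4 is not given, so no misclassification rate can be calculated.

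**The case against.** The case on the other side has real weight.

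- **The list is provisional.** It is called indicative, the site item carries an open note, and the built data dictionary is not shown. This stands as a limit on certainty. But the note asks for finer site categories, not a link to treatment, and permission to change the list does not add the missing field.
- **The limit of one diagnosis is inferred.** The cardinality wording is loose: read literally, "Patient has one or more Complications" would mean that every child has a complication. This stands. It does not remove the problem, because several diagnoses per child would still not tell us which one a treatment addressed.
- **Children with several lesions are never mentioned.** Repeat treatment may mean the same lesion treated again, and a second lesion may share the diagnosis. This stands and limits the reach of the point. No section restricts a child to one lesion, however.
- **The primary outcome is not stratified.** Overall occurrence of complications and technical failure need no lesion key. This stands in full.

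Four stronger readings are tempting, and the documents do not support them.

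- A reader might infer that a second procedure would be analysed under the first lesion's site and condition. No rule says so. The entry might be overwritten, duplicated or left unlinked.
- A reader might infer that the loss is permanent. Records carry a local pseudonym and a treatment date, Trusts keep their own data, and section 10g has investigators review data at least every 6 months. Dates may also help to match some follow-ups to treatments. Recovery from hospital records may be laborious, but nothing shows it to be impossible.
- A reader might cite section 2 on nerves, vessels and solid organs as evidence that risk varies by site. That text compares cryoablation with surgery, not one site with another.
- A reader might put a size on the dilution of differences between sites. Suppose two equal site groups have true complication rates of 20% and 5%, and a share m of procedures in each carries the other's label. The 15-point difference becomes 15 × (1 − 2m), so m = 10% gives 12.0 points. If each affected child has two procedures, one of them mislabelled, and all other children have one, then m = q/(1 + q), where q is the share of children affected. So m = 10% requires q = 0.10/0.90 = 11.1% of all children to have a second treated lesion in the other group. The rates, the symmetry and the shares are all assumed, so the figure carries no weight here.

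**Conclusion.** The point holds as a structural weakness. The stated schema provides no key from a treatment, follow-up or complication to a lesion, so for children treated for more than one lesion the registry data alone cannot reliably support results by site or condition, or change in diameter by lesion. This bears on Objective 4 and secondary outcome 2 and leaves the principal safety result intact.

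The conclusion rests on two assumptions: that the registry is built as section 10c describes, with no further linking field, and that at least some children have more than one lesion treated. The size of the effect depends on how many such children there are. The change is worth making because it is cheap and becomes more laborious as unlinked records accumulate.

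**What to change.** Revise the schema in section 10c so that:

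- a patient has one or more lesions;
- each lesion has one diagnosis, anatomical site, tissue involvement, SNOMED code and biopsy status;
- each treatment names the lesion or lesions treated;
- each lesion size at follow-up names its lesion;
- each complication names its treatment.

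Keep lesion size as a dated measurement at treatment and follow-up, linked to the lesion. Do not reduce it to a single value on the lesion record, because secondary outcome 2 needs both time points. Add a sentence to section 11 that outcomes by site or condition use the treated lesion.

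The cost is one extra selection per treatment or follow-up for children with more than one lesion, and back-filling by the centres of any records already entered. Section 10c already allows items and format to be changed.

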3. AIM(S) OF STUDY

Principle aim: Establish feasibility and safety of cryoablation in children

Secondary aims: Assess response to treatment (as measured by change in lesion size and/or change in symptomatology) post treatment

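### The follow-up items listed in section 10c have no field for other treatment of the lesion or its symptoms after cryoablation, so its effect could not be separated from response

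*Protocol*

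**What the plan says.** Section 3 makes response a secondary aim: "Assess response to treatment (as measured by change in lesion size and/or change in symptomatology) post treatment". Section 9b, item 2, defines the size outcome by "comparing pre-treatment diameter to diameter at 2 years". Items 3 and 4 define change in symptoms and in function after treatment, with no fixed time point. Section 5 describes the registry as non-controlled.

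The dataset in section 10c records treatment in these places:

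- **Before cryoablation:** "Other treatments tried", a list under pre-operative information.
- **Cryoablation itself:** the schema has "Patient has one or more Treatments". The fields of a Treatment record describe probes, freeze and thaw times, cycles, power and technical success.
- **Inpatient stay:** "Any medical support required (list, such as iv analgesia", next to length of stay.
- **Complications:** "Any treatment given", between the duration of the complication and whether it resolved.

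The block headed "Follow-up at 3 mths, 6 mths, 1 year, 2 years" lists date, imaging, size of lesion and symptoms, followed by the complication items. Section 10c adds a caveat about the whole list: "The registry is not limited to these items and the items and data format can be changed before or during the registry".

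**The concern.** The dataset treats other therapy as relevant before cryoablation, but lists no place for it during the two years in which response is measured. Without a control group, the before-after change is the only evidence on efficacy, and it carries the effect of everything given in that interval. A lesion resected at 12 months would have a very small 2-year diameter or none at all. A child who starts regular analgesia may have a better visual analog score. As listed, neither record would look different from a response to cryoablation.

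The consequences reach beyond the overall response summary. Objective 4 in section 4 seeks trends in outcome by condition, and section 13 intends to promote findings about conditions that respond particularly well or badly. If other treatments are more available for some diagnoses than for others, the distortion would differ by diagnosis and could be mistaken for a difference in response. A rule in the analysis plan could not repair this for data that were never entered.

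**Working it through.** The protocol states no figure on this point, so there is none to reproduce. The check sets the listed items against the outcomes.

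**Step 1. Could any listed item hold a later, non-cryoablation treatment of the lesion or its symptoms?**

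| Item in 10c | What it can hold | Holds later lesion or symptom treatment? |
|---|---|---|
| Other treatments, pre-operative block | Therapy before cryoablation | No, except perhaps if re-entered before a repeat cryoablation |
| Further Treatment record | Repeat cryoablation | No; its fields are specific to cryoablation |
| Inpatient medical support | Care during the stay, including iv analgesia | During the stay only |
| Treatment under complications | Treatment of a complication | No, unless the lesion or symptom is itself entered as a complication |
| Follow-up block | Date, imaging, size, symptoms | No |

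**Step 2. Which outcomes depend on the gap?** Diameter (9b, item 2) is exposed to lesion-directed treatment up to 2 years. Symptoms and function (items 3 and 4) are exposed to both lesion-directed and symptomatic treatment, over an interval that is not fixed. Analgesia bears on symptoms, and possibly on function, but not on diameter. The primary outcome, complications, is not the subject of this point.

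**Step 3. Direction, by illustration only.** Suppose response were a yes/no measure, which the protocol does not define. Let r be the true response to cryoablation alone, q the share of non-responders later treated another way, and s the share of those who then meet the measure. All three are assumptions.

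- Later treatment left in: apparent response = r + (1 − r) × q × s.
  - r = 50%, s = 50%, q = 10%: 50 + 50 × 0.10 × 0.50 = 52.5%.
  - r = 50%, s = 50%, q = 40%: 50 + 50 × 0.40 × 0.50 = 60%.
- Those children have no 2-year value and drop out: apparent response = r / [1 − (1 − r) × q].
  - q = 10%: 50/95 = 52.6%.
  - q = 40%: 50/80 = 62.5%.

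Both routes push the result upwards when later treatment goes to non-responders. If responders also receive planned additional therapy and drop out of the 2-year comparison, that part of the error runs the other way. The direction is therefore likely but not certain, and the amount depends entirely on assumed inputs.

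**The case against.** The strongest reply is that the list is not the dataset. Section 10c calls it an indication and leaves it open to change, and it is visibly incomplete: the quality of life questionnaires, visual analog scales and physiotherapy assessment that 9b relies on are not in it, and the schema names a Post-ops entity for which no block is shown. This stands in part. The protocol does not rule the item out, and nobody can say from it that the item will not be collected. But section 5 aims at standardised data from all centres, and an item missing from the only specification shown is not assured at every site. Freedom to change the form makes the repair easy; it does not make it happen.

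It is also fair to say that:

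- Some treatment after the procedure is recorded, namely inpatient support, treatment of complications and repeat cryoablation. A reader might infer that treatment is recorded only before cryoablation, and that goes too far.
- The protocol does not say whether pre-operative information is entered once per child or before each treatment, and the Pre-op list in the Treatment block has unstated content. Either might catch some concomitant therapy.
- How later treatment is handled in the analysis commonly belongs to the analysis plan, which is not at hand. A reader might infer that later treatment is counted as response. No passage states such a rule.
- Exclusion 8b(2), on children offered another modality instead, has no time limit. It most naturally concerns a change of plan before cryoablation. If it were applied afterwards, it would remove failures, which is a selection problem rather than misattribution.
- The 6-monthly data reviews in section 10g give an occasion to add a field, so a reader who concludes that the gap can never be corrected goes further than the text. What would be hard is recovering the information for visits already past.

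**Conclusion.** The point holds in a limited form. The listed follow-up items contain no field for other lesion- or symptom-directed treatment after cryoablation. With the dataset as listed, the secondary response outcomes could not be attributed to cryoablation alone. The conclusion assumes that the registry form follows the list, which the protocol neither confirms nor denies.

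The error would probably favour efficacy, on the assumption that further treatment goes mainly to non-responders. Its size cannot be derived from the document. On one set of assumed values, later treatment left in adds 2.5 to 10 percentage points. Stronger assumptions give more: with r = 50%, s = 80% and q from 20% to 60%, apparent response is 58% to 74% (50 + 50 × 0.20 × 0.80 and 50 + 50 × 0.60 × 0.80). A reader might take such figures as the likely bias, but every input is invented and the protocol defines no responder. They show sensitivity only.

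Nor does the text support the broad reading that analgesia distorts a 2-year response: only diameter is fixed at 2 years, and analgesia affects symptoms. Because response is a secondary aim, this is a change worth making and not a threat to the primary safety outcome.

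**What to change.** 1. Add to each follow-up form a repeating item on other treatment for this lesion or its symptoms since the last visit, with type, start date and reason, and an explicit entry for none.
2. Add to the Treatment form an item for other treatments continuing at cryoablation or given to the lesion in the same session.
3. For the response outcomes in 9b, report the change as observed and, beside it, the change to the last values before any further lesion-directed treatment. Give the number of children so treated by diagnosis. Counting such children as non-responders from that date is another legitimate strategy; whichever is chosen as the main summary should be fixed before the data are seen.
4. State whether exclusion 8b(2) applies after cryoablation has been given, so that failures are not removed from the registry.

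Section 10c already permits changes to the form, so the cost is a few list fields, a little more data entry at each visit and short additions to 9b and 8b. The response summary may become less favourable. The items are best added early, because collecting the information retrospectively across centres would be difficult.
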